6.2.2 Platelet transfusions are associated with risks

Platelet transfusions are independently associated with an increased risk of lung injury, infection, transfusion reactions (highest rate of any blood component) and alloimmunisation, prolonged ICU and hospital length of stay, and mortality^{7,20,21}. Causality is biologically plausible as platelets mediate multiple physiological processes beyond clotting, including interactions with immunological pathways. The systemic inflammatory state of critical illness may predispose, or prime, the immune, endothelial, and coagulation systems, to complications from platelet transfusions²⁰, meaning the ICU population may be more vulnerable to the risks of platelet transfusions than other patient groups.

6.2.3 The evidence to support platelet transfusion in ICU is limited

Clinicians primarily use a low platelet count to decide whether to give a platelet transfusion²². However, despite their common use, it is unclear whether platelet transfusions reduce bleeding in critically ill patients, and if they do at what platelet count transfusion threshold the benefits outweigh the risks of harm. Until recently, the literature on this topic consisted of retrospective cohort studies and two small single centre clinical trials. These studies have many limitations, conflicting conclusions, and by design, are not of a sufficient grade of evidence to inform clinical practice²³⁻²⁸. An updated exploratory meta-analysis which collated data across all trials in different clinical settings found no evidence of an effect of platelet transfusions on reducing bleeding or allcause mortality²⁰, but recognised the lack of data in critical illness In some trial settings there was not only no evidence of a benefit of platelet transfusions on reducing major bleeding or mortality, but signals of harm, for example in critically ill pre-term neonates²⁰.

A recently published, multi-centre, randomised, controlled, non-inferiority trial enrolled 338 patients on the haematology ward or in critical care, with platelet counts of 10-50 x 10⁹/L undergoing insertion of a central venous catheter (CVC) (the PACER trial)²⁹. The authors concluded that withholding a platelet transfusion by adopting a restrictive transfusion policy was associated with more bleeding than platelet transfusion. However, bleeding occurred predominantly in haematology ward patients undergoing subclavian CVC insertion, which is not a common insertion site in many countries or settings³⁰. The risk of bleeding and the efficacy and risk of harms of platelet transfusion in the two patient populations of haematology and critical illness are likely to be different due to differences in the causes of thrombocytopaenia, , and the degree of systemic inflammation^{6,31,32}. This may explain why in the small ICU subgroup, there was no significant reduction in bleeding risk following platelet transfusion. There was also no significant increase in bleeding risk in the severe thrombocytopaenia subgroup (platelet count 10-19 x 10⁹/L) without platelet transfusion, which is inconsistent with the hypothesis that low platelet counts are associated with an increase in bleeding risk.

The primary outcome in the PACER trial was bleeding, and many of the bleeding episodes were Grade 2, often only requiring manual compression. The patient-centeredness of this outcome is questionable, and it only assesses the benefits of a platelet transfusion and does not assess the effect of harms. The ICU subgroup in the PACER trial experienced trends that did not reach the predefined threshold for statistical significance (in this small cohort) for greater incidence of acute lung injury, longer ICU length of stay, and greater mortality, as well as two transfusion reactions to platelets. These outcomes may be more important to patients than non-severe bleeding. By using all-cause mortality as its primary outcome, T4P will measure the combined effect of benefits and harms in ICU patients.

The PACER trial, as all threshold randomised trials of platelet transfusions, was a traditional twoarm trial design, and could only compare the benefits of giving or not giving a platelet transfusion at two, possibly arbitrary, thresholds Two arm trial designs like this, which compare two maximally separated platelet count thresholds below which platelets are transfused (for example 20 versus 50 x 10^9 /L), are unlikely to identify optimal thresholds. To establish the platelet threshold below which platelet transfusion confers a cost-effective patient benefit, T4P uses a novel, randomised adaptive comparative effectiveness design allowing simultaneous study of multiple platelet thresholds to define the optimum threshold by modelling a threshold-response curve.

The uncertainty of when pre-procedure prophylactic platelet transfusions confer benefit over harm has led to variation in clinical practice and guidelines in Australia and globally which may be

resulting in unmeasured harm^{10,20,22,33}. The range of platelet counts over which platelet transfusions are given to critically ill patients prior to a low bleeding risk invasive procedure is wide, although the majority occur in patients with a platelet count in the range < $10-50 \times 10^9/L^{6,8,33-35}$.

6.3 Expected outcomes of the trial

T4P will provide the first and highest-quality evidence of the clinical and economic effectiveness to support a decision on when a pre-procedural, prophylactic platelet transfusion should be administered in ICUs in Australia and internationally. Contributing Australian patients to this international clinical trial will increase the generalisability of the trial results to Australian patients and result in faster translation of the results into clinical practice in Australia. Australia and the UK have a similar approach to platelet transfusion practice. Guidelines for platelet transfusion and specifications by platelet count content are comparable between the two countries. All platelet components, whether apheresis or buffy-coat derived, are leucoreduced, and common practice is to transfuse ABO and RhD identical platelets. Australian participation in the trial will also allow for an economic evaluation from the perspective of the Australian healthcare system, as well as enhance Australian clinical trial infrastructure and capacity. Ultimately, T4P will inform policy and clinical practice to improve outcomes for patients and to ensure the most effective and efficient use of donated platelets.

7 Study design

7.1 Aim

To define the optimum platelet threshold below which platelets should be transfused prior to an invasive procedure in critically ill patients (Figure 1), and to explore whether the optimum threshold differs according to patient characteristics.

7.2 Hypothesis

That platelet transfusion in critically ill patients has net clinical and monetary benefit only below certain thresholds where any gain of preventing bleeding exceeds harm from exacerbating inflammatory and/or infective processes.

7.3 Objectives

- To model the threshold-response curve for the effect of platelet transfusion prior to/during an invasive procedure in critically ill patients (Figure 2 and in the Simulations Appendix at https://www.icnarc.org/Our-Research/Studies/Current-Studies/T4P/About).
- To evaluate whether the optimum value of the threshold-response curve varies according to patient characteristics.
- To evaluate the cost-effectiveness of standardisation of practice to the optimum threshold versus current usual practice, including an Australian economic evaluation.

7.4 Study design

Open label, randomised, Bayesian adaptive comparative effectiveness trial across five equally spaced thresholds of thrombocytopenia ($<10 - <50 \times 10^9/L$).

7.5 Primary outcomes

- Clinical effectiveness: All-cause mortality at 90 days.
- Cost-effectiveness: Incremental costs, QALYs and net monetary benefit at 90 days.

7.6 Secondary outcomes

- Mortality at discharge from ICU, hospital and at one year
- Survival to longest available follow-up
- Rates of major and fatal bleeds classified according to the HEmorhage MEasurement (HEME) bleeding score¹
- Venous and arterial thromboses in hospital and to one year
- Duration of renal, advanced cardiovascular and advanced respiratory support according to UK Critical Care Minimum Data Set (CCMDS) criteria
- Length of critical care unit and acute hospital stay
- Health-related quality of life (EQ-5D-5L questionnaire at 90 days and one year)
- Resource use and costs at 90 days and one year
- Net monetary benefit at one year

7.7 Australian sites

Just under 20% (around 500 patients) of the total study participants will be recruited from approximately 20 Australian ICUs over 3 years. Study interventions will occur in the admitting ICU, or where in the hospital the procedure takes place if it precedes an ICU admission.

7.7.1 Australian site requirements

- Compliance with all responsibilities as stated in the T4P Clinical Trial Research Agreement
- Compliance with all requirements of the Australian trial protocol
- Compliance with the principles of Good Clinical Practice (GCP)

7.7.2 Australian site responsibilities

- Identify a Principal Investigator (PI) to lead the T4P trial locally
- If possible, appoint an Associate/Sub PI to assist with the running of the T4P trial locally
- Identify a T4P research coordinator responsible for day-to-day local trial coordination
- Agree to incorporate T4P into routine critical care clinical practice, highlighting the importance of systematic screening for potential eligible patients and prompt randomisation
- Agree to adhere to individual patient randomisation allocations (unless safety concerns) and ensure adherence with the trial protocol
- Agree to aim to randomise all eligible patients at the time of decision to admit to ICU and to maintain a Screening Log
- Agree to train all staff who undertake low bleeding risk procedures to randomise patients into the trial
- Agree to data collection requirements

7.7.3 Australian site initiation and activation

The following must be in place prior to a site being activated for recruitment:

- A completed site initiation visit (held in person or virtually)
- All relevant institutional approvals (e.g. site research governance authorisation)
- A fully signed T4P Clinical Trial Site Agreement

• A completed Delegation Log

Once the Australian coordinating centre has confirmed that all necessary documentation is in place, a site activation e-mail will be issued to the Principal Investigator (PI), at which point, the site may start to screen for eligible patients. Once the site has been activated, the PI is responsible for ensuring:

- Adherence with the most recent approved version of the trial protocol
- Training of relevant site staff in accordance with the trial protocol and GCP requirements
- Appropriate means to identify and randomise eligible patients into the trial
- Timely data collection, entry, and validation
- Prompt notification of all serious adverse events (SAEs)

All local staff (i.e., PI, Associate/Sub PI, local investigators, research teams) involved in the conduct of the trial must be trained to carry out their assigned roles. Site research staff should be signed off by the PI on the Delegation Log, once trained, and the Delegation Log copied and sent to the Australian coordinating centre whenever changes are made.

Staff members solely involved in the screening and randomisation of patients should be provided with trial-specific training to carry out these tasks and recorded on the Training Log (full GCP training will not be required for these staff members).

7.8 Participants

Critically ill adults admitted to, or requiring admission to, an ICU who have low platelet counts (< 50 x 10^{9} /L) prior to an invasive procedure of low bleeding risk.

To be eligible for the T4P Trial, patients must meet all the inclusion criteria, and none of the exclusion criteria **at the time of randomisation**:

7.8.1 Inclusion criteria

- 1. Adult (aged \geq 18 years)
- 2. Accepted for admission or admitted to a participating ICU
- 3. Platelet count < 50×10^9 /L
- 4. Planned to undergo a **specified** low bleeding risk invasive procedure OR platelet transfusion considered for an **'other'** low bleeding risk procedure

Specified low bleeding risk invasive procedures include the following:

- CVC insertion (including vascular access for renal replacement therapy)
- Paracentesis/superficial abdominal fluid collection drainage
- Pleural aspiration

'Other' procedures may be included if the clinician deems these to be a low bleeding risk invasive procedure and a platelet transfusion is being considered for the procedure. These include, but are not limited to:

- Arterial catheter insertion
- Arterial or central venous catheter removal
- Pleural drain
- Interventional radiology

- Bronchoscopy with or without lavage
- Wound dressing changes
- Surgical procedures where the clinical team agree risk of bleeding is low, e.g. re-look laparotomy, or wound closure

7.8.2 Exclusion criteria

- 1. Ongoing major haemorrhage requiring blood products and/or surgical/radiological intervention[†]
- 2. Intracranial haemorrhage within prior 72 hours⁺
- 3. Contra-indication to platelet transfusion (such as thrombotic microangiopathies; heparininduced thrombocytopenia; immune thrombocytopenia; congenital platelet function defects)
- 4. Acute promyelocytic leukaemia (APML)
- 5. Known advance decision refusing blood/blood component transfusions (e.g. Jehovah's Witnesses)
- 6. Death perceived as imminent or admission for palliation
- 7. Previously randomised into T4P
- 8. Fulfilled all the inclusion criteria and none of the other exclusion criteria \ge 72 hours

⁺Exclusion criteria 1 and 2 are dynamic, if resolved, the patient may be reconsidered for the trial.

Patients undergoing procedures not eligible for randomisation will remain available for inclusion where subsequent eligible procedures occur.

7.9 Co-enrolment

Co-enrolment will be permitted with observational studies (including those collecting samples) without prior agreement needed.

The T4P investigators will consider co-enrolment of participants into other interventional studies where there is no possible conflict with the T4P objectives. Co-enrolment agreements will be put in place on a trial-by-trial basis.

8 Study procedures

8.1 Screening

At the point of the decision to admit to an ICU, potentially eligible patients will be screened against the inclusion and exclusion criteria by the local clinical team, supported by the site research team. Screening Logs will record enrolled patients, reasons for exclusion and the reason eligible patients are not enrolled.

Once admitted to an ICU, patients with platelet counts \geq 50 x 10⁹/L will be screened daily until recruitment, refusal, or ICU discharge. Once a patient first meets all inclusion criteria and none of the exclusion criteria, they should be randomised within 72 hours.

8.2 Randomisation

Randomisation will occur as soon as possible (< 72 hours) after confirming eligibility. Randomisation will be performed by the site investigator, research coordinator or delegated staff at each site. Patients will be randomised to one of five platelet thresholds using a central web-based randomisation service, available 24 hours/seven days per week.

Following randomisation into T4P, each participant will be assigned a unique T4P Trial Number and a case report form (CRF) will be completed by the local team.

Enrolment in the study must be documented in the participant's medical record in accordance with local policy and practices.

8.3 Interventions

Patients will be randomised to one of five equally spaced platelet thresholds ($<10 - <50 \times 10^9$ /L) (Figure 3), below which they would receive a single adult equivalent dose (AED, defined according to national specifications) of platelet transfusion delivered before or during the procedure.

Treatment according to the randomly allocated threshold will continue for all subsequent low bleeding risk invasive procedures until ICU discharge (i.e. all low bleeding risk procedures for which the patient's most recent platelet count is below the allocated threshold). If a patient is readmitted to an ICU during the index hospital stay within the 90 days, treatment according to the randomly allocated threshold will be recommenced. Procedures occurring after ICU discharge are at discretion of the clinical team and do not need to follow the allocated treatment threshold.

Randomisation and group allocation are independent of baseline platelet count. The treating clinician will be notified of group allocation immediately following randomisation so they can determine whether the participant should or should not receive a pre-procedure platelet transfusion on the initial and subsequent occasions. For example, if a participant is randomised to the $<30 \times 10^9$ /L group, the randomisation notification will tell the treating clinician: "The threshold for platelet transfusion is: Less than 30×10^9 /L". If the participant's initial platelet count is 19 x 10^9 /L, then they should be given a single unit platelet transfusion before the first procedure (the procedure that determined eligibility for the trial) and for any subsequent procedure where their platelet count is $<30 \times 10^9$ /L. If the participant's platelet count is 30×10^9 /L prior to a subsequent low bleeding risk procedure, then they should not receive a transfusion. There is no requirement to recheck the platelet count following the pre-procedure platelet transfusion.

8.4 Co-interventions

All other care will be provided at the discretion of the treating clinical team.

Where a patient is receiving a low bleeding risk invasive procedure, platelet prophylaxis is only permitted according to allocated randomised threshold. Where significant bleeding occurs during or after a low bleeding risk invasive procedure, or where platelets are given outside of any procedure, platelet administration should follow local guidance. Platelets are permitted for high bleeding risk interventional procedures.

8.5 Monitoring adherence to the intervention

Adherence to the trial protocol will be assessed by comparing, for each threshold, both the proportion of patients who crossed their assigned threshold prior to a planned procedure and (correctly) received a platelet transfusion before the procedure, and the proportion who did not cross their threshold prior to a planned procedure and (correctly) did not receive a transfusion before the procedure. Adherence will be assessed separately with respect to each patient's first procedure and any subsequent procedures.

Protocol non-adherence will be defined as:

- Receipt of platelet transfusion for low bleeding risk procedure when platelet count is above randomly allocated threshold
- Platelet transfusion not received for low bleeding risk procedure when platelet is below randomly allocated threshold

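### The adherence proportions in 8.5 count only transfusions before the procedure, although the intervention allows a dose during it, and the first non-adherence bullet misses a transfusion at exactly the threshold

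*Protocol*

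**What the plan says.** **The intervention.** Protocol 8.3 and the synopsis (Intervention) specify a single adult equivalent dose "of platelet transfusion delivered before or during the procedure" when the count is below the allocated threshold. The first objective in 7.3 concerns the "effect of platelet transfusion prior to/during an invasive procedure in critically ill patients". The worked example in 8.3 settles the tie: in the <30 group, a patient whose count is exactly 30 "prior to a subsequent low bleeding risk procedure, then they should not receive a transfusion".

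**The adherence proportions.** Section 8.5 sets out two, compared across thresholds. The first covers patients who "crossed their assigned threshold prior to a planned procedure and (correctly) received a platelet transfusion before the procedure". The second covers those who did not cross their threshold and "correctly) did not receive a transfusion before the procedure".

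**The non-adherence bullets.** The same section then defines non-adherence as:

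- Bullet 1: "Receipt of platelet transfusion for low bleeding risk procedure when platelet count is above randomly allocated threshold"
- Bullet 2: "Platelet transfusion not received for low bleeding risk procedure when platelet is below randomly allocated threshold"

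Neither bullet limits when the dose is given.

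**Related rules.** Under 8.4, prophylactic platelets for a low-risk procedure must follow the allocated threshold, but platelets for significant bleeding during or after it follow local guidance.

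**The concern.** The treatment rule and the rule that measures compliance with it do not match. A clinician who gives the dose during the procedure has done what 8.3 asks, yet the first proportion does not credit it. The proportions and the bullets also use different timing, so 8.5 can score one procedure in two ways. Separately, bullet 1 starts strictly above the threshold and bullet 2 strictly below it, so a transfusion at exactly 10, 20, 30, 40 or 50 breaches 8.3 but meets neither definition.

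What is at stake is the reported adherence. The DMEC monitors protocol adherence (9.1), and site-visit timing rests on a risk assessment that includes each site's adherence (13.2.2). Neither section says whether it uses the proportions or the bullets, so an effect on either is possible but not established.

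**Working it through.** The protocol states no adherence figure to reproduce. The check has two parts: scoring each case under each rule, then showing the direction and possible size of the timing error.

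**1. Scoring the cases**

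| Case | 8.3 and 8.4 | 8.5 proportions | 8.5 bullets |
|---|---|---|---|
| Below threshold, dose given during the procedure | Compliant | Not counted as correct | Not non-adherent |
| Above threshold, prophylactic dose during | Breach | Counted as correct | Non-adherent (bullet 1) |
| Exactly at threshold, dose before | Breach | Not correct | Not non-adherent |
| Exactly at threshold, prophylactic dose during | Breach | Counted as correct | Not non-adherent |

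The last two rows read *did not cross* in the second proportion as including a count equal to the threshold. On that reading, a tie dosed before the procedure already fails the second proportion, so the tie error as such lies in bullet 1. A tie dosed during the procedure is missed by both measures.

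**2. Direction and size of the timing error**

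The protocol supplies none of these inputs; all are assumed.

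- p: share of below-threshold patients given a dose (before or during)
- q: share of patients above threshold given a prophylactic dose
- d: share of those doses given during the procedure

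The denominators are taken as all patients below threshold and all patients above it.

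- First proportion as written: p(1 − d). True value p, so it is understated by p·d.
- Second proportion as written: 1 − q(1 − d). True value 1 − q, so it is overstated by q·d.

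With p = 90% and q = 10%, both true values are 90%:

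| d | First proportion | Second proportion |
|---|---|---|
| 0% | 90% | 90% |
| 5% | 85.5% | 90.5% |
| 10% | 81% | 91% |
| 20% | 72% | 92% |

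Over p = 80–95%, q = 5–20% and d = 0–20%:

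- First proportion: understated by 0 to 19 points (0.95 × 0.20 = 0.19).
- Second proportion: overstated by 0 to 4 points (0.20 × 0.20 = 0.04).

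Patients correctly dosed during the procedure stay in the denominator of the first proportion and lower it, but bullet 2 does not call them non-adherent.

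**3. Comparison across arms**

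Entry requires a count below 50, so at the eligibility count every patient in the <50 arm falls under the first proportion, which is understated. In lower arms more patients fall under the second, which is overstated. The error therefore need not be equal across the thresholds being compared.

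**4. Ties**

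One integer count per arm escapes bullet 1. How often a transfusion occurs there cannot be sized, because the protocol gives no platelet-count distribution. In the <50 arm a tie cannot occur at the eligibility count.

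**The case against.** The strongest reply is that *before* is the protocol's shorthand. Section 8.3 itself, after allowing a dose during the procedure, refers to "whether the participant should or should not receive a pre-procedure platelet transfusion", and the aim in 7.1 uses similar language. The formal definition of non-adherence is the bullet list, which handles timing correctly. In the second proportion, looking only before the procedure may have a purpose: it keeps platelets given for bleeding, which 8.4 permits, from being scored as breaches. Treatment at a tie is not ambiguous, since the clinician is told the threshold is less than 30. Deviations must also be recorded on the CRF (section 14), so the underlying breaches are not lost.

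Much of this stands as mitigation. The bullets are sound on timing, and the bleeding rationale, though unstated, is plausible for the second proportion; what remains wrong there is the narrow case of a prophylactic dose given during the procedure. But that rationale cannot explain the first proportion, where the restriction removes compliant doses. Shorthand is harmless in an aim but not in a measurement rule, where literal wording decides what is counted. Clear instructions to clinicians and a deviation log do not correct the proportions or the word *above*.

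**Conclusion.** The concern holds and is minor. The mismatch between 8.5 and 8.3, and the gap in bullet 1, follow from the text alone and are certain. The clearest error is in the first proportion. The size is unknown: the 0 to 19 and 0 to 4 point ranges are arithmetic on assumed inputs, not expected effects, and the timing error vanishes if no doses are given during procedures. The primary analysis is by intention to treat (10.3), and neither the adaptations (10.5) nor the stopping provisions (10.6) depend on the adherence measures. Only the reported adherence, and any use made of it in monitoring, is exposed.

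**What to change.** Change the wording of 8.5 in three places:

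- In each of the two proportions, replace the reference to transfusion before the procedure with *before or during the procedure (excluding platelets given for significant bleeding under 8.4)*.
- In bullet 1, replace *above* with *at or above*.

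The proportions and the bullets then score the single rule stated in 8.3, and platelets given for bleeding are excluded explicitly.

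The cost is these edits and a matching change to the adherence derivation. The derivation must separate prophylactic from bleeding-related platelets. Section 12.3 lists adherence and bleeding-response data only in general terms, so confirm that the CRF records the timing and indication of each dose.
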